#### 5.5.4.3 *QT/QTc values according to plasma concentrations of P03277*

Concentration-response relationship will be investigated between  $\Delta$ QTc and P03277 concentrations using a mixed model approach.

This analysis will be performed on the Per Protocol Set including all time points for which a pair of  $\Delta$ QTc and P03277 concentrations is available.

#### Graphical exploration:

In order to assess quality of QTcF correction before and after dosing the following figures will be provided:

- Scatter plot of QTcF (y-axis) versus RR (x-axis) for baseline and placebo data with a regression line
- Scatter plot of  $\Delta$ QTcF (y-axis) versus  $\Delta$ RR (x-axis) for values collected during P03277 treatment periods with a regression line.

In both cases, the regression lines should tend toward an horizontal line, otherwise, a dependency still exist between QTcF and RR and QTcPOP may be considered as preferred dependent variable.

The following exploratory plots will also be performed before starting the modelling:

- Scatter plot of individual  $\Delta$ QTc values vs. time-matched concentrations including a nonparametric trend curve will be provided to assess the pattern of the relationship
- Scatter plot of individual  $\Delta$ HR values vs. time-matched concentrations including a nonparametric trend curve will be provided to detect impact of the treatment on HR
- Time course of  $\Delta\Delta$ QTc by dose level as calculated during the primary criteria analysis
- Time course of  $\Delta\Delta$ HR (or  $\Delta\Delta$ RR) by dose level as calculated during the secondary criteria analysis

The SAS syntax corresponding to the scatter plot of change in QTc vs. concentrations including a trend curve is:

```
proc sgplot data = dataset ;
  scatter x=Concentrations y=CHG/ transparency=0.6 group=TRT name="p1"
  legendlabel="Individual Delta QTc-Concentration pairs";
```

CONFIDENTIAL	STATISTICAL ANALYSIS PLAN N° GDX-44-006  VERSION N° 2.0      DATED: 24JUL2018  	  Page 30 / 57
--------------	--	---

```

loess x= Concentrations y=CHG/ nomarkers smooth=0.3 name="p2"
legendlab="Trend line" lineattrs=(color=green);
refline 0/axis=y;
label TRT="Actual treatment";
xaxis grid label="Concentration Unit";
yaxis grid label="ms";
keylegend "p1" "p2";
run;

```

Model development:

The model development will start with the pre-specified mixed linear model as detailed in Garnett et al. [1] considering  $\Delta QTcF$  as dependent variable. In case of the graphical exploration suggests that Fridericia correction does not account for all RR variation,  $\Delta QTcPOP$  will be used instead.

Placebo data will be considered for the analysis with concentration values set to 0. Moreover, concentrations below the limit of quantification will also be set to 0.

The fixed effect parameters of the pre-specified model will be intercept, slope for P03277 concentrations, influence of baseline (centered on mean) on intercept, treatment specific intercept (0=P03277, 1=Placebo), and theoretical timepoints post-administration. Subject specific random effects will be added on intercept and slope parameters with an unstructured covariance matrix. In case of the unstructured covariance matrix is not supported by the data, other simplified or reduced structures will be investigated (ex. variance components).

$$\Delta QTc_{ijk} = (\theta_0 + \eta_{0,i}) + TRT_j + (\theta_1 + \eta_{1,i})C_{ijk} + TIME_k + \theta_2(QTc_{ijk=0} - \overline{QTc_0}) + \varepsilon_{ijk} \quad (1)$$

Where  $i$  is the subject,  $j$  the treatment and  $k$  the time.

The  $\Delta\Delta QTc$  and their 2-sided 90% confidence intervals will be calculated at P03277 0.1 mmol/kg and 0.3 mmol/kg  $C_{max}$  geometric means as follows:

$$\Delta\Delta QTc_i = (TRT_0 - TRT_1) + \theta_i C_{max_i}$$

The SAS syntax corresponding to Equation 1 and  $\Delta\Delta QTc$  estimation is:

```

proc mixed data = dataset method = REML plots=all;
ods output estimates=EST solutions=SOL CovParms=COV;
class Trt Time subj;
model  $\Delta QTc$  = Baseline Trt Concentration Time / ddfm = kr solution alphap=.05
residual outp=ipred outpm=pred;
random INT Concentration/ subject = subj type = un;

```

CONFIDENTIAL	STATISTICAL ANALYSIS PLAN N° GDX-44-006  VERSION N° 2.0      DATED: 24JUL2018  	  Page 31 / 57
--------------	--	---

Estimate " $\Delta\Delta QTc$  P03277 0.1 mmol/kg" *Trt* 1 -1 *Concentration*  $C_{max_1}$  /  $\alpha = 0.1$  cl;

Estimate " $\Delta\Delta QTc$  P03277 0.3 mmol/kg" *Trt* 1 -1 *Concentration*  $C_{max_2}$  /  $\alpha = 0.1$  cl;

run;

No additional covariate investigation will be performed and in order to avoid unnecessary model-building steps, non-significant fixed parameters will not be removed from the model, unless they cause problem of convergence or estimability issues. Random effects not supported by the model will be remove as they may result in non-convergence problems.

Model evaluation:

Goodness of fit plots will be provided, consisting on:

- QQ plot of residuals
- Concentrations versus residuals
- Time, baseline and treatment versus residuals

Any marked bias in residual plots may suggest model misspecification. Moreover, a large and significant treatment specific intercept (TRT term in the model) may also indicate model misspecification (i.e. lack of linearity).

In addition, structural model hypothesis will be checked from graphical exploratory plots:

- The absence of effect on HR will be investigated from time course of  $\Delta\Delta QTc$  by dose level
- The hypothesis of direct relationship will be evaluated from the time course of  $\Delta\Delta QTc$  by dose level. If the primary analysis allow to reject the hypothesis of QT/QTc prolongation, hysteresis phenomenon will not be considered, otherwise, hysteresis will be investigated by visual inspection comparing time of peaks in QT response and concentrations
- The hypothesis of linear relationship between  $\Delta QTc$  and concentrations will be evaluated from exploratory scatter plot and the goodness of fit plots.

In case of the linear relationship between  $\Delta QTc$  and P03277 concentrations cannot be accepted, an alternative model such as saturable model will be considered.

$$\Delta QTc_{ijk} = (\theta_0 + \eta_{0,i}) + TRT_j + \frac{(\theta_1 + \eta_{1,i})c_{ijk}^Y}{(\theta_2 + \eta_{2,i})^Y + c_{ijk}^Y} + TIME_k + \theta_3(QTc_{ijk=0} - \overline{QTc_0}) + \varepsilon_{ijk}$$

(2)

In Equation 2, the parameter  $\theta_1$  is the maximum asymptotic effect due to treatment, and the parameter  $\theta_2$  is the concentration at which the effect is half  $\theta_1$ .

In case of a hysteresis phenomenon cannot be discarded, an effect compartment model combining a population PK model on P03277 and a PKPD model will be envisaged.

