### 2.2.2. Secondary cardiac safety criteria

Secondary cardiac safety criteria included to support the primary endpoint are the followings:

- Parameters measured at any timepoints:
  - QT (ms)
  - QTcPOP (ms), Qtc according to population specific correction formula
  - QTcB (ms), QTc according to Bazett's formula
  - RR (ms)
  - QRS (ms)
  - PR (ms)
  - Heart rate (bpm)
  - Interpretation
  - Sinus rhythm (yes/no)
- Morphological analysis:
  - Changes in T and U wave morphologies will be described through the description of morphological abnormalities (Q or QS pattern, axis and voltage, hypertrophy, ST depression and elevation, T/U wave abnormalities, AV conduction, intraventricular conduction defects, rhythm, technical quality). Changes from baseline that represent the appearance or worsening of the morphological abnormality will be analysed.

QTcPOP will be obtained using a linear mixed modelling of QT interval (ms) vs RR interval (ms) on all available extracted Holter ECG from placebo period data.

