#### SAS Procedure:

```
proc mixed data = dataset method = REML;
  class subj ;
  model  $\log(QT) = \log(RR) /$  SOLUTION ddfm = kr;
  random subj / type = cs;
run;
```

The slope will determine the correction formula of QTcPOP:  $QT/RR^\alpha$  where RR interval is in seconds. The correction derived from placebo period will be applied to all trial products data.

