#### Decision rule

The impact of P03277 on QT/QTc prolongation will be considered as below the threshold of regulatory concern if the upper bound of the 90% confidence interval of  $\Delta\Delta\text{QTc}$  predicted at supra-clinical dose  $C_{\text{max}}$  is below 10 ms.

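### The first plot used to judge Fridericia correction (SAP 5.5.4.3) fits one line with no stated subject term, so between-subject differences can tilt or flatten it and misdirect the choice between QTcF and QTcPOP in the concentration-QTc model

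*SAP*

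**What the plan says.** Before fitting the concentration-QTc model, SAP 5.5.4.3 (Graphical exploration) checks Fridericia with two figures. The first is a "Scatter plot of QTcF (y-axis) versus RR (x-axis) for baseline and placebo data with a regression line", on absolute values. The second plots ΔQTcF against ΔRR "for values collected during P03277 treatment periods with a regression line". The criterion is visual: "In both cases, the regression lines should tend toward an horizontal line, otherwise, a dependency still exist between QTcF and RR". The SAP gives no slope limit, confidence interval or test, and it states no subject term for either line.

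The consequence is worded in two ways. Under Graphical exploration, "QTcPOP may be considered as preferred dependent variable". Under Model development, the condition "In case of the graphical exploration suggests that Fridericia correction does not account for all RR variation" leads to a firm instruction that ΔQTcPOP replaces ΔQTcF.

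Elsewhere the SAP does allow for subject. The model that estimates the QTcPOP exponent (SAP 2.2.2) contains "random subj / type = cs", and the concentration-QTc model has subject random effects on intercept and slope. The chosen variable then feeds a separate decision rule: the drug's effect "will be considered as below the threshold of regulatory concern if the upper bound of the 90% confidence interval" of the predicted ΔΔQTc at the supra-clinical Cmax lies below 10 ms.

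**The concern.** A rate correction should remove the dependence of a person's QT on that person's own RR. A single line through all subjects' absolute QTcF and RR values also reflects which people have long QTcF and which have slow hearts. That association says nothing about the correction. Sex is one possible source, since each sequence has six men and six women.

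Such a line can therefore tilt when Fridericia is right, or look flat when it is wrong. At stake is the dependent variable of an analysis with its own 10 ms rule. It would be chosen after the data are seen, from a plot that partly answers a different question.

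**Working it through.** The plan gives no figure for this check, so there is none to reproduce.

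**Inputs from the documents.** 48 subjects (SAP 3.3). In the placebo period there are 11 post-dose times (SAP 1.2) and three pre-dose times (SAP 5.5.1.1), so m = 14 records per subject.

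**Assumed, not in the documents.** QTcF SD between subjects s_b = 10 to 20 ms (central 15) and within subjects s_w = 7 ms. RR SD between subjects r_b = 110 ms and within subjects r_w = 60 ms. Fridericia exact within every subject, and no true association between subject means. Tilt means slope × 400 ms RR.

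**1. Line fitted within subjects.** SD of tilt = 400 × s_w / (r_w √(48 × 13)) = 400 × 7 / (60 × 24.98) = 1.87 ms.

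**2. Pooled line.** V = 110² + 60² = 15,700. Three parts add in squares (central case):
- chance association of subject means: 400 × 110 × 15 / (√48 × V) = 6.07 ms
- residual noise: 400 × 7 × √V / (√672 × V) = 0.86 ms
- between-subject QTcF against within-subject RR: 400 × 15 × 60 / (√672 × V) = 0.88 ms

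SD of tilt = √(6.07² + 0.86² + 0.88²) = 6.19 ms. The first part dominates and depends on the number of subjects, not on records per subject, so extra baseline records would hardly change it.

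**3. How often the tilt passes a cutoff** (normal approximation; the cutoffs are illustrative):

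| Line | SD of tilt (ms) | > 4 ms | > 8 ms |
|---|---|---|---|
| Pooled, s_b = 10 | 4.2 | 34% | 6% |
| Pooled, s_b = 15 | 6.2 | 52% | 20% |
| Pooled, s_b = 20 | 8.2 | 63% | 33% |
| Within subject | 1.9 | 3% | <1% |

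Simulation agrees closely. With s_w = 9 ms, the within-subject σ in SAP 3.3, the within-subject SD becomes 1.87 × 9/7 = 2.4 ms and its share above 4 ms about 10%. The pooled results barely move.

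**4. A true association between subject means.** For correlation ρ the expected pooled slope is ρ s_b r_b / (r_b² + r_w²). A second simulation used r_b = 100 ms, s_w = 9 ms and 15 records. With ρ = 0.3 and s_b = 15, the slope is 0.3 × 15 × 100 / 13,600 = 0.033 ms per ms, or 3.3 ms per 100 ms RR (simulated 3.2 to 3.3). The within-subject line stayed at 0 (SD about 0.6 per 100 ms), and so did the change-scale plot.

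**5. Masking.** If the true exponent is 0.25, the QTcF slope near RR = 1 s and QTc = 400 ms is 400 × (0.25 − 1/3) = −33 ms per s, or −3.3 ms per 100 ms. An opposing ρ = 0.3 adds +3.3, so the pooled line is flat on average. In simulation its mean was −0.07 (SD 1.62), and it lay within ±1 ms per 100 ms in 46% of trials.

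**6. What a wrong choice costs.** For an exponent error e and a heart rate rising from 60 to 60 + d bpm, ΔQTc shifts by 400 × [((60 + d)/60)^e − 1].
- False switch: the SAP 2.2.2 mixed model kept the exponent at 0.319 to 0.347 on average (SD 0.016 to 0.018). Taking e = 0.02 gives 0.64 ms (5 bpm) and 1.24 ms (10 bpm).
- Misfit missed, exponent 0.25: e = 1/12 gives 2.7 ms (5 bpm) and 5.2 ms (10 bpm).

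**The case against.** The strongest reply is that this is a visual check on exploratory plots for a secondary model. Most of that stands.

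A reader might infer that any tilt automatically replaces the endpoint. The text does not say so. The lines need only tend toward horizontal, and the first statement of the consequence is permissive. The later, firmer sentence still depends on what the plots are judged to suggest.

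A reader might take the 52% in the central case as a false-switch rate. It is not one. The SAP has no 4 ms limit, a tilt of 4 ms over 400 ms is only 1 ms per 100 ms, and few would see it in a wide scatter. At 8 ms the share is 20%.

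A reader might also infer that the whole check is confounded. It is not. The second plot removes each subject's level and would be expected to show a misfit hidden in the first. Since both lines should be flat, a missed switch would require the reader to discount that second plot, for example by blaming its tilt on the drug. The same requirement, however, means that a flat second plot does not override a tilted first one.

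Finally, the SAP does not state how the line is fitted. A single pooled fit is the natural reading of one regression line on a scatter plot. If something else is meant, the SAP should say so.

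**Conclusion.** The point holds, at minor-to-moderate priority. The first plot is confounded by between-subject differences and is a weak basis for choosing the dependent variable. Under the assumed variances its line varies roughly two to four times as much as a within-subject line (SD 4 to 8 ms against 2 ms over 400 ms RR). The frequencies rest on those assumptions. The mixing of the two relations does not.

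The effect stays within the secondary concentration-QTc model. The primary by-timepoint analysis uses QTcF with no switch, and QTcPOP is already analysed in the same way as a secondary endpoint (SAP 5.5.4.1), so the documents do not support a reading that the trial's main conclusion is at risk. A false switch costs about 1 ms or less for moderate heart-rate changes, because the QTcPOP exponent is itself estimated with a subject term. A missed misfit would cost more, about 2.7 to 5.2 ms in the example, but needs the second plot to be set aside as well.

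**What to change.** For the first plot, replace the pooled line by the RR slope and its confidence interval from a mixed model of QTcF on RR with a subject random intercept, fitted to the same baseline and placebo records. SAP 2.2.2 already uses this form. A plot of subject-centred QTcF against subject-centred RR would serve as the display.

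Base the move to QTcPOP on that slope, with a numeric criterion written down before unblinding, and state how the second plot counts if the two disagree. Reconcile the permissive wording under Graphical exploration with the mandatory wording under Model development.

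The cost is one short additional model and a few sentences in the SAP. No data collection, sample size or primary analysis changes.

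### SAP 5.5.4.3 switches off the hysteresis assessment when the primary analysis passes, so the secondary concentration-QTc estimate could be biased by a small delayed effect without being flagged

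*SAP*

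**What the plan says.** SAP 5.5.4.3 sets out the concentration-response analysis. "The model development will start with the pre-specified mixed linear model", with change from baseline in QTcF as the response. The fixed effects are an intercept, a slope on concentration, centred baseline, a treatment-specific intercept "and theoretical timepoints post-administration". The effect at a given time depends on the concentration at that same time, so this is a direct-effect model. The saturable fallback (Equation 2) is direct as well.

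Under Model evaluation, the direct-relationship hypothesis is to be judged from the time course of placebo-corrected QTc by dose. The next sentence adds the condition: "If the primary analysis allow to reject the hypothesis of QT/QTc prolongation, hysteresis phenomenon will not be considered". Only when the primary analysis fails does the SAP compare, by eye, when the QTc response peaks with when the concentration peaks. If hysteresis cannot be ruled out, "an effect compartment model combining a population PK model on P03277 and a PKPD model will be envisaged".

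The Decision rule gives the analysis its own conclusion: the drug's impact "will be considered as below the threshold of regulatory concern if the upper bound of the 90% confidence interval" of the prediction at the supra-clinical peak concentration is below 10 ms.

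**The concern.** The condition uses a result about size to settle a question about timing. Rejecting a 10 ms prolongation at every timepoint and both doses shows that any effect is small. It does not show that there is no effect, or that the effect follows plasma concentration without delay.

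The design makes timing relevant. P03277 is an intravenous bolus (protocol 5.1.1), time zero is the end of injection (protocol 8.1.3.3), and the first post-dose sample is at 5 min (SAP 2.3.2.1). Peak sampled concentration should therefore fall at or near 5 min, and an effect that peaks later does not fit Equation 1.

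After a primary pass, the SAP closes both the comparison of peak times and the route to the effect-compartment model. At stake are the reported slope, the predictions at peak concentration and their intervals, which could match neither the true maximum nor the true effect at peak concentration.

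**Working it through.** **Inputs from the documents** (protocol 11.2; SAP 3.2, 3.3 and 4): within-subject SD 9 ms, expected difference 2 ms, margin 10 ms, one-sided 5%, power 85%, 40 evaluable subjects of 48 randomized, L = 9 in the sample-size calculation, and 11 post-dose timepoints in the SAP's primary analysis.

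**1. The plan's own sample size.** N = 2 × (t_α + t_β′)² × (9/8)², with β′ = 1 − 0.85^(1/L) and N − 2 degrees of freedom.
- L = 9: β′ = 0.0179; 2 × (1.688 + 2.181)² × 1.2656 = 37.9, so 38, within 2 of the stated 40.
- L = 11: β′ = 0.0147; 2 × (1.686 + 2.265)² × 1.2656 = 39.5, so 40.

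The stated 40 is reproduced closely enough for its inputs to be used below.

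**2. What a primary pass allows.** The standard error per timepoint is 9 × √(2/40) = 2.01 ms. The 90% half-width is 1.686 × 2.01 = 3.39 ms. An observed effect up to 10 − 3.39 = 6.6 ms passes (6.9 ms at N = 48).

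This is a limit on the observed estimate. Simulated pass probabilities for a true delayed peak, at N = 40 with an assumed within-period correlation of 0.5, are:

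| True peak (ms) | 3 | 4 | 5 | 6 | 7 | 9 |
|---|---|---|---|---|---|---|
| Primary passes | 89% | 77% | 58% | 39% | 20% | 3% |

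At zero correlation they are lower: 39–48% for 5 ms over several assumed kinetics, and 17% for 6 ms in the one setting run.

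**3. Bias of the direct-effect model.** *Assumed, not in the documents:* plasma half-lives of 5 min and 1–2.5 h, an effect-compartment half-life of 1–4 h, effect proportional to dose, and a true maximum of 6 ms at 0.3 mmol/kg reached at 1.5–4 h. Mean profiles for both doses and placebo at the 11 timepoints were fitted by least squares with time as a factor, a treatment intercept and a slope.

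| Effect-compartment half-life | Predicted at the 5-min concentration |
|---|---|
| 1 h | 4.76–4.82 ms |
| 2 h | 3.95–4.00 ms |
| 4 h | 3.24–3.35 ms |

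Against 6 ms this is short by 1 − 4.82/6 = 20% up to 1 − 3.24/6 = 46%. The true 5-min effect is 0.50–1.42 ms, so the prediction is also too high there, by at least 3.24 − 1.42 = 1.8 ms. With no delay the same fit returns 6.0 ms, so the delay causes the bias.

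**4. A second set of assumptions.** For a true 5 ms delayed peak (plasma half-life 1–3 h, delay half-life 0.5–4 h), the noise-free prediction is 2.4–4.8 ms and the true 5-min effect 0.2–1.6 ms. Simulations with noise, random intercept and slope, and delay half-life 0.5–2 h, restricted to trials that passed the primary, gave:
- upper 90% bound below the true 5 ms peak: 42–90% (7–10% with no delay);
- upper 90% bound below 10 ms: 100%;
- treatment intercept significant: 9–40%.

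**5. Peak time alone as a criterion.** With no drug effect and exchangeable noise, each of the 11 timepoints is equally likely to show the observed maximum. It falls away from 5 min with probability 10/11 = 91%, and at 1 h or later (7 of 11 timepoints) with probability 7/11 = 64%.

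**The case against.** The strongest reply is that the condition removes less than it seems to.

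- **The assumption is still looked at.** The sentence just before the condition, which has the direct relationship judged from the time course, applies in all cases. So do the time-course plots "by dose level as calculated during the primary criteria analysis", the concentration scatter with a trend curve, the residual plots ("Time, baseline and treatment versus residuals") and the treatment-intercept warning. A reader might infer that nothing checks for delay after a pass; the documents do not support that. These checks are weak substitutes, however. In a balanced fit, the time factor forces residuals pooled by time to average zero. The SAP reads a large treatment intercept as non-linearity. And it says hysteresis will not be considered even if the plot shows a late peak.
- **The primary result is unaffected.** A reader might infer that the trial would miss or misplace a delayed effect. It would not: the by-timepoint estimates at both doses, out to 24 h, report its size and timing. Study success (SAP 3.8) rests on the primary analysis and assay sensitivity. This stands fully.
- **The illustration is larger than the plan expects.** At the planned 2 ms, a bias of 20–46% is 0.4–0.9 ms, small beside the 3.39 ms half-width. Nothing in the documents suggests a delayed QTc effect of P03277. This stands as a limit on size.
- **The condition guards against chasing noise.** Step 5 shows that peak time alone would often signal a lag when there is no effect. This stands, and it shapes the fix. It does not justify tying the check to the primary result.

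**Conclusion.** The concern holds for the secondary concentration-QTc analysis only. The SAP lets a pass against a 10 ms margin stand in for evidence that any effect is undelayed, and those are different questions. Observed effects up to about 6.6 ms can pass. Should one be delayed, the slope, the prediction at peak concentration and its 90% interval can be biased: 3.2–4.8 ms predicted for a true 6 ms maximum. That size rests wholly on assumed plasma and effect kinetics.

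Two stronger readings should be set aside. The first is that a true effect near 6.6 ms would usually pass. That figure limits the observed estimate; a true 6 ms delayed peak passes in a minority of simulated trials, and when it fails the SAP's check does run. The second is that the 10 ms conclusion is at risk. The model's upper bound stayed below 10 ms in every simulated trial that passed the primary. The point is worth correcting because the remedy is cheap and protects reported estimates from an assumption that is not properly tested.

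**What to change.** In SAP 5.5.4.3, Model evaluation, delete the condition on the primary result. State that hysteresis is assessed in all cases by comparing the time courses of placebo-corrected QTc and of concentration, dose by dose.

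Pre-specify a lag criterion that noise alone will rarely meet. An example is a QTc peak later than the concentration peak, with a minimum mean effect size, and consistent across neighbouring timepoints. Peak time alone should not be enough. The thresholds can be set by simulation under no effect and under a direct effect.

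If the criterion is met: flag the direct-effect prediction as unreliable, present the by-timepoint maximum and its interval beside it, and fit the effect-compartment model the SAP already names as a sensitivity analysis. If it is not met, keep the pre-specified model.

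The cost is a short SAP edit. The concentration data, the QTc time-course plots and the fallback model are already planned. The downside is a little more analysis work and, occasionally, a flag raised by chance.
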